6.5 Safety Oversight

- The study Sponsor's Medical Director will serve as Medical Monitor, and will review all reported adverse events, including all cases of severe hypoglycemia and DKA, and adverse device effects that are reported during the study. SAEs typically will be reviewed within 1 working day of reporting. Other AEs typically will be reviewed on a weekly basis.
- The Medical Monitor will determine if the events require expedited reporting to FDA, IRB and/or all
- participating sites. In addition, the Medical Monitor will confirm the MedDRA code assigned and
- adjudicate events as specified in the safety management plan for relatedness to the study procedure and
- 810 investigational device, assess seriousness and severity, and determine if the event the event is anticipated
- or unanticipated. Both the investigator's and Medical Monitor's assessments will be recorded, however,
- the adjudication decision of the Medical Monitor will be used for the final classification of events,
- including relatedness to the study procedures and/or the investigational device, for the determination of
- safety endpoints and for all regulatory reports, product labeling, and publications or presentations.

6.6 Stopping Criteria

6.6.1 Participant Discontinuation of Study Device

- In the case of an unanticipated system malfunction resulting in a severe hypoglycemia or DKA event (or a malfunction that could have led to severe hypoglycemia or DKA), use of the study device will be suspended for that participant while the problem is diagnosed. The UADE will be reported to the IRB and FDA. After assessment of the problem and any correction, use of the study device will not be restarted
- until approval is received from the IRB and FDA.
- In the absence of a device malfunction, use of the study device by a participant will be discontinued if any of the following occur:
- The investigator believes it is unsafe for the participant to continue on the intervention. This could be due to the development of a new medical condition or worsening of an existing condition; or participant behavior contrary to the indications for use of the device that imposes on the participant's safety
- The participant requests that the treatment be stopped
- Participant pregnancy
- One distinct episodes of DKA in the study treatment period as defined in section 6.2.4
- One distinct severe hypoglycemia events in the study treatment period as defined in section 6.2.3
- Each DKA or severe hypoglycemia event will be reviewed by the Medical Monitor with respect to
- determination of cause and whether the occurrence of the event can be attributed to use of the study
- device or study drug.

6.6.2 Criteria for Suspending or Stopping Overall Study

- In addition to the suspension of device use due to a UADE as described in section 6.6.1, study activities
- could be similarly suspended if the manufacturer of any constituent study device requires stoppage of
- device use for safety reasons (e.g. product recall). The affected study activities may resume if the
- underlying problem can be corrected by a protocol or system modification that will not invalidate the
- results obtained prior to suspension.
- Closed-loop system use will also be suspended if there are five or more cases of severe hypoglycemia or
- five or more cases of DKA across the entire study in participants who have initiated Control-IQ
- technology 2.0 use. The IRBs and FDA will be notified. After assessment of the problem and any
- corrections are implemented, use of the closed-loop system may be restarted if approval is received from
- the IRBs and FDA.

846

835

815

816

847	Chapter 7: Miscellaneous Considerations
848	7.1 Drugs Used as Part of the Protocol
849 850	Subjects will use their own Humalog (insulin lispro) or Novolog (insulin aspart) during the Run In and Treatment Period with the study devices.
851	7.2 Collection of Medical Conditions and Medications
852 853 854	Pre-Existing Conditions : Any medical condition that is either present at screening, a chronic disease, or a prior condition that could impact the participant's health during the course of the study (e.g., prior myocardial infarction or stroke) will be recorded.
855 856	Medical Conditions Developing During the Study : Medical conditions developing during the study will be reviewed by the investigator for their relationship to the study device.
857 858 859 860	Medications : All medications in use at the time of screening or added during the course of the study will be recorded. Nutraceuticals and preventative treatment also will be recorded. Medications only taken as needed either can be recorded when prescribed or only recorded if used during the study. Glucagon for treatment of severe hypoglycemia will only be recorded if used during the study.
861	7.3 Prohibited Medications, Devices, Treatments, and Procedures
862 863 864	Treatment with any insulin other than Humalog or Novolog insulin with the study pumps is not permitted. Treatment with a non-insulin glucose -lowering agent, other than metformin, is not permitted, including GLP-1 agonists, Symlin, DPP-4 inhibitors, SGLT-2 inhibitors, sulfonylureas.
865 866 867 868	The investigational study devices (t:slim X2 insulin pump with Control-IQ technology 1.5 or 2.0) and study sensor and transmitter (Dexcom CGM sensor and transmitter) must be removed before magnetic resonance imaging (MRI), computed tomography (CT) or diathermy treatment. Participants may continue in the trial after temporarily discontinuing use if requiring one of the above.
869	7.4 Rescue Medications, Treatments, and Procedures
870 871	Each participant will be required to have a glucagon preparation for rescue therapy for severe hypoglycemia.
872	7.5 Pregnancy Reporting
873 874 875	If pregnancy occurs, the participant will be discontinued from the study. The occurrence of pregnancy will be reported to the Coordinating Center within seven days and to the IRB as an Unanticipated Problem within seven calendar days.
876	7.6 Participant Compensation
877	Participant compensation will be specified in the informed consent form.
878	7.7 Participant Withdrawal
879	Participation in the study is voluntary, and a participant may withdraw at any time. For participants who
880	withdraw, their data will be used up until the time of withdrawal.
881	

Chapter 8: Statistical Considerations

8.1 General Statistical Considerations

Summary statistics will be generated for all relevant variables. In the comparison of continuous variables, distributions will be tested for the normality assumption. If standard parametric techniques are found to be inadequate, an appropriate non-parametric technique will be used. Categorical variables will be presented using frequencies and percentages and compared using differences in proportions unless stated otherwise. For safety/adverse event reporting, both the number of overall events and the number of subjects experiencing that event will be tabulated. No corrections will be made for multiple testing procedures. All analyses will be conducted using SAS® version 9.4 or higher. Although this study features a crossover design, it will be assumed for the exploratory purposes of this analysis that there are no residual period effects and no carryover effects present. The correlated nature of data collected by the same subject across multiple conditions will be accounted for in the statistical modeling, such as using a paired t-test for

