- Concurrent use of any non-insulin glucose-lowering agent, other than metformin (for example, GLP-1 agonists, Symlin, DPP-4 inhibitors, SGLT-2 inhibitors, sulfonylureas).
- 6. Hemophilia or any other bleeding disorder
- 7. Hemoglobinopathy
- 8. History of heart, liver, lung or kidney disease determined by investigator to interfere with the study
- 9. History of allergic reaction to Humalog or Novolog
- 10. Use of any medications determined by investigator to interfere with study
- 11. Significant chronic kidney disease (which could impact CGM accuracy in investigator's judgment) or hemodialysis
- 12. Concurrent use of any medication that could interfere with the study CGM, such as hydroxyurea
- 13. History of adrenal insufficiency
- 14. History of abnormal TSH consistent with hypothyroidism or hyperthyroidism that is not appropriately treated
- 15. History of gastroparesis
- A condition, which in the opinion of the investigator or designee, would put the participant or study at risk
- 17. Participation in another pharmaceutical or device trial at the time of enrollment or anticipated for during the time period of study participation
- 18. Employed by, or having immediate family members employed by Tandem Diabetes Care, Inc., or having a direct supervisor at place of employment who is also directly involved in conducting the clinical trial (as a study investigator, coordinator, etc.); or having a first-degree relative who is directly involved in conducting the clinical trial

Participant Duration

Approximately 6-12 weeks

Study Endpoints

The adult, pediatric and preschool populations will be combined for the analysis of primary and secondary endpoints. Separate analyses also will be performed for the adult, pediatric and preschool cohorts for the primary and secondary endpoints. CGM data collected during the challenge periods will not contribute to overall analysis of CGM metrics. The three study time periods are the Run-In period with Control-IQ technology 1.5, treatment period with Control-IQ technology 2.0 at the standard target, and treatment period with Control-IQ technology 2.0 at the lower target, where the order of treatment periods will be randomized.

Primary Endpoints:

- Severe hypoglycemia (with cognitive impairment such that assistance of another individual is needed for treatment) during study compared with data on severe hypoglycemic events reported by T1D Exchange clinic registry over a 3-month time period

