3.3 Visit 6: Control-IQ 2.0 Training Visit

- After participants complete the run-in, they will return for the Control-IQ 2.0 training visit, and switch to
- the Control-IQ 2.0 study pump after training by qualified staff.
- Control-IQ 2.0 allow for selection of different glycemic targets, as well as toggling autoboluses in
- standard and exercise activity. The late bolus feature will also be available.
- Participants will be randomized to use either a daytime 30-min predictive glucose target of 90-130 mg/dL
- or 112.5 to 160 mg/dL for the first two-week period, then switch to the other target after 2 weeks.
- In the training visit, participants will:

327

328

329

332

337

345

346

347

348

349

350

351

352

353

354

355356

357

358

- 1) Select the appropriate target in clinic on their study pump per the randomization, and will be instructed by study staff to use the assigned glycemic target during each two week period.
 - 2) Be instructed that autoboluses will default to on during normal activity, and off during exercise activity.
 - 3) Be reminded again that use of the security PIN on the insulin pump will be required for anyone who is not entirely responsible for their own diabetes care, to include all 2-5 year olds, and those 6 years of age or older who may be only partially responsible for their own diabetes management.
 - 4) Be instructed that sleep activity will be required during Control-IQ 2.0 use. A sleep schedule should be programmed into the pump for use each night. Participants will be instructed to disable sleep or adjust the schedule on the nights of the late bolus meal challenges, then re-enable sleep activity as soon as the challenges are over, so it is used the rest of the night.
 - 5) Review prior training guidelines from the Control-IQ technology 1.5 training visit, and be taught how the new features are different in Control-IQ technology 2.0.
 - 6) Review the study meal late bolus challenges, to be performed twice in each two week period. Participants may also use late bolus as desired outside of the challenges.
- The participant will be given a User Guide as a reference as well as review the Hypoglycemia and
- Hyperglycemia Treatment Guidelines as part of the Study Participant Instruction Sheet. The study device
- training form will be completed.
- Participants will be instructed to download the study device prior to each phone contact or office visit.

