8.3 Sample Size

comparing continuous outcomes.

The sample size of at least 30 adults and adolescents age 14+ years old, 30 children age 6-13 years old, and 12 preschool participants age 2-5 years of age who will complete the trial was selected to have a reasonable time period of use in each age cohort to establish safety, with each subject completing 2 weeks of Control-IQ 1.5 technology use, 2 weeks of Control-IQ 2.0 technology use with the target of 112.5 to 160 mg/dL, and 2 weeks of Control-IQ 2.0 technology use with the target of 90-130 mg/dL. The choice of sample size is not based on statistical principles. In addition, the sample size assures a reasonable number of late bolus meal challenges completed.

There is a further enrollment goal of at least half of all participants in each age group have an HbA1c at baseline of $\geq 7.5\%$, and have at least 6 participants age 14-17.

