2. CGM hypoglycemia outcomes, compared between the three study time periods 922 a. Overall % time <54 mg/dL 923 b. Overall % time <70 mg/dL 924 3. Times in ranges-overall (70-180 mg/dL, >180 mg/dL, >250 mg/dL, 70-140 mg/dL) compared 925 between the three study time periods 926 4. Mean glucose compared between the three study time periods. 927 5. Overall variability (CV and SD) compared between the three study time periods 928 6. Secondary endpoints 2 - 5 compared during daytime and nighttime, across the three study time 929 930 periods 7. Secondary endpoints 2 - 5 as well as adverse events, during the study meal challenge periods, for 931 late bolus feature use compared to normal bolus in the meal challenges. 932 8. Time to intervention for hypo- or hyperglycemia during the study meal challenge periods, for late 933 bolus feature use compared to normal bolus in the meal challenges. 934 935 9. Number of interventions for hypo- or hyperglycemia during the study meal challenge periods for late bolus feature use compared to normal bolus in the meal challenges. 936 10. Subgroup Analysis for all metrics by age cohort, baseline HbA1c cohort (HbA1c at baseline of > 937 7.5%, yes/no), and target activity use (standard target, lower target, sleep activity, exercise 938 939 activity). 940 8.5 Analysis Datasets 941 942 Safety analysis set: All participants who initiate the Treatment Period and use the study device at least one time (including training). 943 CGM analysis set: Any member of the Safety Analysis Set who has at least 24 hours of CGM data during 944 945 either Treatment Period. CGM data occurring within the meal challenge windows (from time of start of meal up to 5 hours afterwards [3 hours for age 2-5]) will not be used to determine whether a subject is 946 included in CGM analysis set or not. 947 948 Late bolus meal challenge set: Any member of the Safety Analysis Set who has at least 24 hours of CGM data during the Treatment Period, and who has at least 3 hours of CGM data for at least one meal 949 challenge. 950 8.6 Analysis of Endpoints 951 8.6.1 Analysis of the Safety Event Endpoints 952 953

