8.6.3 Analysis of CGM Endpoints

CGM metrics will be assessed in CGM analysis set, and computed for the Run-In and both Treatment Periods separately. CGM metrics will be computed per subject over 24 hours, during daytime (6am-11:59pm), and during nighttime (12am-5:59am), as well as by age cohort (adults/adolescents, children 6 – 13, and preschool), baseline HbA1c cohort (HbA1c at baseline of ≥ 7.5%,yes/no), and target activity use as specified by the device (standard target, lower target, sleep activity, and exercise activity). The main statistical comparison will be made between the three 2-week periods (Run In, Treatment

The main statistical comparison will be made between the three 2-week periods (Run In, Treatment Period at standard target, Treatment Period at lower target). The comparison will be pairwise – Run-in vs standard targe, Ru-in vs lower target, and standard vs lower target. The percent time in glycemic ranges will be calculated as the number of measurements in the specified range divided by the total number of measurements for which it can be determined whether or not the measurement was in specified range.

The "Low" and "High" CGM readings will be included in all analyses. Percent time will be compared using a paired t-test assuming sufficient normality assumptions hold, otherwise an appropriate non-parametric method will be utilized.

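### The randomised standard-versus-lower target comparison of continuous CGM metrics has no period term and should carry one

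*Combined protocol and SAP*

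**What the plan says.** The Synopsis (Study Endpoints) describes a run-in on Control-IQ 1.5 and two Control-IQ 2.0 periods, one per target, "where the order of treatment periods will be randomized". Section 3.3 repeats the randomisation. Neither gives an allocation ratio, blocking or stratification.

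Section 8.1 states that "it will be assumed for the exploratory purposes of this analysis that there are no residual period effects and no carryover effects present". Section 8.6.3 makes three pairwise comparisons, including standard versus lower target, "using a paired t-test assuming sufficient normality assumptions hold", and otherwise uses an unnamed non-parametric method. No period term, sequence term or period-adjusted sensitivity analysis appears.

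The comparison is repeated by cohort: "Separate analyses also will be performed for the adult, pediatric and preschool cohorts". Section 8.3 sets the minimum completers: "The sample size of at least 30 adults and adolescents age 14+ years old, 30 children age 6-13 years old", and 12 preschool participants. Section 8.2 says that p-values will be calculated but not used for formal inference.

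**The concern.** Randomising the order allows the target effect to be separated from a change over time that all participants share. The planned test makes no such separation. A shared change is possible: at the 2.0 training visit (section 3.3) participants are to "be taught how the new features are different in Control-IQ technology 2.0", so the first 2.0 period is their first use of those features in this study, and section 3.7 lets investigators adjust pump settings as the study proceeds. The documents give no size for such a change.

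If there is one, a paired test places it in the residual variance when the sequences are equal, and partly in the estimate when they are not. The analysed split can be uneven by chance or through loss. Section 8.5 admits to the CGM set "Any member of the Safety Analysis Set who has at least 24 hours of CGM data during" either 2.0 period, a paired test needs both, and section 8.15 plans no imputation. In cohorts of 30 and 12, a difference of a few participants is a large fraction.

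**Working it through.** **Inputs.** N = 72 completers (30 + 30 + 12; Synopsis, section 8.3) and a two-sided 5% level (section 8.16). The plan has no power figure to reproduce, because section 8.3 says that the sample size has no statistical basis. Assumptions: SD is the standard deviation of the within-participant standard-minus-lower difference apart from any period shift; d is the shift from the first to the second 2.0 period; r = d/SD takes the values 0.1, 0.25, 0.5 and 1; the splits n1:n2 are illustrative.

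**Model.** The standard-minus-lower difference has mean τ − d when the standard target comes first and τ + d when it comes second.

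- Plain paired mean: absolute bias = d|n1 − n2|/N; true standard error = SD/√N.
- Period-adjusted estimate (average of the two sequence means): no bias; standard error = SD√(N/(4·n1·n2)), with N − 2 degrees of freedom.

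**Equal sequences.** The two estimates are the same number. The paired test's variance absorbs d², so its reported standard error is too large by a factor of about √(1 + r²): 1.005, 1.031, 1.118 and 1.414. In simulation at 36:36, with τ set for 80% adjusted power, plain power is 79.7%, 78%, 73% and 51%. Its false-positive rate is 4.9%, 4.3%, 2.8% and 0.6%.

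**Unequal sequences.** False-positive rates of the plain test are simulated. The last column is the ratio of adjusted to plain 95% interval width when d = 0: √(N²/(4·n1·n2)) × t(N−2)/t(N−1).

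| Split | Bias | False positive, r = 0.25 / 0.5 / 1 | Width ratio |
|---|---|---|---|
| 36:36 | 0 | 4.3% / 2.8% / 0.6% | 1.0002 |
| 40:32 | 0.11d | 4.9% / 4.7% / 3.4% | 1.0065 |
| 44:28 | 0.22d | 6.6% / 10.4% / 18.7% | 1.026 |
| 18:12 | 0.20d | 5.2% / 5.4% / 4.6% | 1.022 |
| 20:10 | 0.33d | 6.6% / 10.0% / 17.0% | 1.062 |
| 8:4 | 0.33d | 5.3% / 5.4% / 5.1% | 1.074 |

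Repeated simulations differ by a few tenths of a point; the highest value seen at 40:32, 18:12 or 8:4 was 5.6%. The adjusted test stays near 5% throughout.

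**Hand check, 44:28 at r = 0.5, in SD units.** Bias = 0.5 × 16/72 = 0.111. True standard error = 1/√72 = 0.118. Reported standard error ≈ 0.118 × √(1 + 0.25 × 4·44·28/72²) = 0.131. The rejection limit is 1.994 × 0.131 = 0.261. The upper-tail probability is P(Z > (0.261 − 0.111)/0.118) = P(Z > 1.27), about 10%, in line with the simulation.

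**How likely are such splits?** Under assumed simple 1:1 allocation, the binomial probability of a split at least as uneven as 44:28 among 72 is 7.6%, and of 20:10 among 30 is 9.9%. Blocking would lower both.

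**Where adjustment is less accurate.** Setting r²(n1 − n2)²/N² + 1/N equal to N/(4·n1·n2) gives a break-even r = √(N/(4·n1·n2)): 0.12 at 40:32 and at 44:28, 0.19 at 18:12 and at 20:10, 0.31 at 8:4. Below these values the plain estimate has the smaller root-mean-square error.

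**The case against.** The strongest reply is that the plan is candid. The assumption is stated and tied to an exploratory purpose, section 8.2 has no formal hypotheses, and no power is claimed that could be lost. At r of 0.1 to 0.25 with equal sequences the overstatement is only 0.5% to 3%, and larger r is neither supported nor excluded. Two weeks on version 1.5, whose changes 2.0 incorporates (section 1.1.2), may also reduce novelty at the first 2.0 period. All of this stands and limits the weight. It does not justify leaving out the term: p-values and intervals will still be reported, and the term is cheap near balance.

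Five stronger readings are tempting but unsupported.

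- A reader might infer that the target comparison is biased as planned. With equal sequences it is not, and randomised order is what secures that.
- A reader might infer that false positives are generally inflated, or that they always stay near 5%. Both fail: the result depends on the split.
- A reader might see a conflict between the paired test and section 7.7, which says that for participants who "withdraw, their data will be used up until the time of withdrawal". There is none, because those data can still enter safety tables and period summaries.
- A reader might take section 8.16 to prescribe an unpaired rank-sum test. It names that test only as an example, and section 8.1 commits to respecting within-participant correlation.
- A reader might extend the point to the run-in contrasts. Run-in always comes first, so run-in versus 2.0 is a non-randomised before-after comparison that a 2.0 period term cannot correct. That is a separate matter.

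**Conclusion.** The point holds for the continuous CGM endpoints and the standard-versus-lower contrast only. If a period shift exists, equal sequences give an unbiased estimate with an overstated standard error; unequal analysed sequences give a bias of d|n1 − n2|/N, with material false-positive inflation at splits such as 44:28 or 20:10 once r reaches about 0.5. Whether a shift exists, and how large it is, cannot be read from the documents; every size above rests on assumed r and assumed splits. The contrast is secondary and exploratory and the primary endpoints are safety events, so this is a worthwhile correction of modest weight. Carryover, the other half of the section 8.1 assumption, is not assessed here.

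**What to change.** In section 8.6.3, specify for this contrast on continuous CGM metrics a linear mixed model with target and period (first or second 2.0 period) as fixed effects and participant as a random effect. With complete pairs this is equivalent to a two-sample comparison of period differences between sequences. Report the number analysed per sequence and the period estimate with its 95% confidence interval. If normality fails, apply the rank-sum test to first-minus-second-period differences between sequences. In the preschool cohort, show the unadjusted paired result alongside.

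In section 8.1, withdraw the no-period-effects assumption for this continuous contrast only. The event proportions (8.6.1) and the Cox and log-rank comparison (8.6.4.2) are outside this change and keep the stated assumption.

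The cost is SAP wording, one degree of freedom and a little reporting. With no period effect the interval widens by 0.02% at 36:36, 0.65% at 40:32, 2.6% at 44:28, 2.2% at 18:12, 6.2% at 20:10 and 7.4% at 8:4. At unequal splits adjustment is also the less accurate choice when r is below the break-even values, which is why the preschool results should appear both ways. Keeping participants with only one 2.0 period is a minor extra: for 66 pairs plus 6 such participants, the standard error falls by 0.25% to 1.7% at assumed between-period correlations of 0.9 to 0.3, and this relies on data missing at random.
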